4.2 Handing of Missing Data

To reduce the incidence of missing data, sites and subjects will be trained in methods to encourage continued participation to maximize the completion rate and overall quality of the trial. With regard to the primary efficacy variable, IOP, there are steps taken in the procedure for collecting these data to minimize the likelihood of spurious data.

Missing data will not be imputed.

4.3 Adjustment for Multiplicity

To account for the multiple comparisons of the primary endpoints, adjustment for multiplicity will be fulfilled by using a hierarchical testing, based on a fixed-sequence procedure defined in Table 1.

First, the primary endpoint is tested for non-inferiority at all 5 time points at Day 28 and all 4 ontreatment time points at Day 1 for the first pre-defined Group comparison listed in Table 1. If the upper limit of the 2-sided 95% CI of the difference between H-1337 and Timolol is strictly lower than the value 1.5, then non-inferiority is concluded. If non-inferiority is concluded at the 9 timepoints, then testing of the second listed Group Comparison in Table 1 can take place at the 2-sided alpha level of 0.05. Otherwise, non-inferiority cannot be concluded and no further formal testing takes place.

The same sequential approach is then applied to the remaining endpoints listed in Table 1. Endpoints are tested in the order defined in Table 1.

For the first 3 rows in Table 1, non-inferiority at the 1.5 threshold at all 9 timepoints must be shown to allow to proceed to the next row. For the last 3 rows in Table 1, non-inferiority at the 1.0 threshold at 5 or more timepoints must be shown to allow to proceed to the next row.

Table 1 Pre-defined Sequence for Hierarchical Testing

Order	Group Comparison	Non-Inferiority Criteria
1	H-1337 1.0% Ophthalmic Solution b.i.d. vs	1.5 threshold at all 9 time points
	Timolol 0.5% Ophthalmic Solution b.i.d	
2	H-1337 0.6% Ophthalmic Solution b.i.d vs	1.5 threshold at all 9 time points
	Timolol 0.5% Ophthalmic Solution b.i.d	
3	H-1337 1.0% Ophthalmic Solution q.a.m. vs	1.5 threshold at all 9 time points
	Timolol 0.5% Ophthalmic Solution b.i.d	
4	H-1337 1.0% Ophthalmic Solution b.i.d. vs	1.0 threshold at 5 or more time points
	Timolol 0.5% Ophthalmic Solution b.i.d	
5	H-1337 0.6% Ophthalmic Solution b.i.d vs	1.0 threshold at 5 or more time points
	Timolol 0.5% Ophthalmic Solution b.i.d	
6	H-1337 1.0% Ophthalmic Solution q.a.m. vs	1.0 threshold at 5 or more time points
	Timolol 0.5% Ophthalmic Solution b.i.d	

4.4 Disposition

The number and percentage of subjects enrolled (signed informed consent), randomized, and the number of subjects who receive at least one dose of IP will be summarized by treatment groups and overall. The following additional summaries will be presented:

- The number and percentage of subjects included in the Safety Analysis population, the ITT population and the PP population;
- The number and percentage of subjects who complete the study;
- The number and percentage of subjects who withdraw from the study and the reason for withdrawal;
- The number and percentage of subjects with a protocol violation and with a major protocol violation:
- The number and percentage of subjects who attend a study visit, for each study visit.

Percentages will be calculated on the number of subjects who are randomized.

4.5 Washout Period

A listing including information on whether a subject enters the washout period or not, the type of used ocular hypotensive therapy and the length of the washout period will be created for each subject in the Safety Analysis Population.

4.6 Demographics and Baseline Characteristics

Gender, age, ethnicity, race and iris colour will be summarized by treatment groups and overall.

Age will be calculated as the number of years, as an integer value, from date of birth to the date of the informed consent signature. In other words, age is the truncated integer of the difference between date of birth and the date of the informed consent signature.

Baseline IOP, BCVA and central corneal thickness (measured by pachymetry) will be summarised by treatment group (and overall) and eye (study eye and fellow eye). Central corneal thickness will be calculated as the mean of the 3 collected measurements.

Gonioscopy

The number and percentage of subjects with a confirmed normal anatomy will be summarized by treatment group (and overall) and eye. In addition, the number and percentage of subjects within each category of the Shaffer grade will be summarized by treatment group (and overall) and eye (study eye and fellow eye).

Visual Fields

The number and percentage of subjects with a normal, abnormal not clinically significant and abnormal clinically significant visual fields assessment will be summarized by treatment group (and overall) and eye (study eye and fellow eye). This will be calculated on the subgroup of eyes with a visual fields assessment meeting the protocol definition of reliability.

Summaries will be presented for the Safety, ITT and PP populations.

4.7 Medical and Ocular History

Medical and ocular history will be coded using the Medical Dictionary for Regulatory Activities (MedDRA) Version 26 or higher.

The number and percentage of subjects under each medical history term, coded by system organ class (SOC) and preferred term (PT), will be summarized by treatment for the safety population. Ocular history will also be presented on both the study eye and the fellow eye. All percentages will be based on the number of subjects or eyes in the safety population within each treatment group. If a subject has a medical/ocular history term more than once, the subject will be counted only once under any given SOC or PT.

4.8 Prior and Concomitant Medications

All medications will be coded using the World Health Organization drug dictionary (WHODRUG) version January, 2023 or higher.

Incidence of prior and concomitant medication will be presented by treatment, Anatomical Therapeutic Chemical (ATC) Level 4 and PT for the safety population. Ocular medication will be presented on both the study eye and the fellow eye combined.

Prior medications are those that start and stop before exposure to treatment. Concomitant medications are all medications taken during the study period, including those started before but ongoing at the time of the first IP dose.

A subject with more than one occurrence of the same medication in a particular ATC class will be counted only once in the total of those reporting medications in that particular ATC class.

4.9 Concomitant Procedures

Procedures will be coded using the MedDRA Version 26 or higher.

The number and percentage of subjects under each procedure term, coded by SOC and PT, will be summarized by treatment for the safety population. Percentages will be based on the number of subjects in the safety population within each treatment group. If a subject has a procedure term more than once, the subject will be counted only once under any given SOC or PT.

4.10 Treatment Exposure

The number and percentage of subjects by number of missed doses will be summarized by eye and treatment. In addition, the number of missed doses will be summarized by eye and treatment using summary statistics for continuous variables.

Duration of drug exposure is defined as the number of days a subject receives an IP dose. The number and percentage of subjects in each category will be summarized by eye and treatment. The categories are: <7 days, 7 to <14 days, 14 to <21 days, 21 to <28 days, ≥28 days.

4.11 Efficacy Analyses

All efficacy analyses will be performed using both the ITT and PP populations. Missing values will not be imputed.

4.11.1 Primary Efficacy Analyses

Change from Baseline in IOP (mmHg) at Day 28 and Day 1 (on-treatment time points) in the study eye is the primary efficacy endpoint. It will be summarized by timepoint and treatment group in the ITT population primarily and in the PP population secondarily. The endpoints will be analysed using an analysis of covariance (ANCOVA) model including baseline value and treatment groups as independent variables. The least square (LS) means, standard error (SE) and 2-sided 95% CI will be reported for each treatment group at each post-randomization visit.

In addition, the differences between treatments (H-1337 vs Timolol) will be calculated for each H-1337 treatment group. A time-matched longitudinal model adjusting for baseline and including a random effect for subject will be used to calculate the LS mean, SE, and 2-sided 95% CI for the between-treatments differences. The model will also be tested for treatment by visit and treatment by time points interactions. If no interactions are detected, the main effect model will be used. The variance-covariance matrix-structure used in the model will be the unstructured (TYPE=UN). If convergence is not achieved, a compound-symmetry structure will be used (TYPE=CS).

The testing procedure for non-inferiority will be performed as described in Section 4.3.

Missing values will not be imputed.

All summaries generated for IOP will be using the mean/median value recorded in the case report form.

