4.3 Subject Withdrawal and/or Discontinuation

Subjects are free to discontinue their participation in the study at any time without prejudice to further treatment. The investigator must withdraw any subject from the study at their request. Subjects should provide the reason for withdrawal and confirm whether they are withdrawing consent or withdrawing from IP treatment. The investigator or D. Western Therapeutics, Inc. designee, may withdraw the subject from IP treatment for any reason or if the subject meets any of the following criteria.

- Experiences a serious or intolerable AE that is judged by the investigator to preclude further study participation.
- Develops a clinically significant laboratory or other abnormality that is judged by the investigator to be potentially related to IP.
- Requires a medication that is prohibited by the protocol. Contact the Medical Monitor to discuss exiting a subject due to use of a prohibited medication before exiting the subject.
- Does not follow the protocol procedures, including noncompliance.
- Is lost to follow-up; every effort should be made to contact the subject.
- Administrative reasons, including termination of the trial by the Sponsor, unavailable for follow-up procedures.
- Experiences glaucomatous progression and/or unacceptable IOP elevation, per the discretion of the investigator.

Should a subject's medical or mental condition change or become unstable during the study, such that the ability of the subject to continue in this study becomes compromised or, in the investigator's judgment, their health is jeopardized, or further continuation is unadvisable, the subject may be withdrawn from study treatment.

If a subject withdraws or is withdrawn from IP treatment, every effort should be made to ensure the subject continues to participate in the remaining trial visits.

If a subject withdraws or is withdrawn from IP treatment, either at her/his request or at the discretion of the investigator or D. Western Therapeutics, Inc. the reason for withdrawal should be recorded. All subjects withdrawing or withdrawn from IP dosing, regardless of cause, will return within 14 days from their last dose of IP to complete Early Termination visit assessments; consult the Medical Monitor to determine which diurnal measurements, if any, are required for the ET visit.

Version Date: 19 Jan 2024

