4.11.2 Secondary Efficacy Analyses

The secondary efficacy endpoints are all related to IOP in the study eye.

Change from Baseline in IOP at Day 7 and Day 14 in the study eye will be summarised by visit, timepoint and treatment group. The endpoints will be analyzed using an ANCOVA model including baseline value and treatment groups as independent variables. The LS means, SE and 2-sided 95% CI will be reported for each treatment group at each post-randomization visit.

In addition, the differences between treatments (H-1337 vs Timolol) will be calculated and summarised by visit, timepoint and treatment group (for each of the H-1337 groups). The ANCOVA model will be used to calculate the LS mean, SE, and, 2-sided 95% CI for the between-treatments differences.

Similar analyses will be performed for the following endpoints:

- IOP.
- percentage change from Baseline in IOP,
- mean diurnal IOP (12-hour diurnal),
- change from Baseline in mean diurnal IOP (12-hour diurnal),
- percentage change from Baseline in mean diurnal IOP (12-hour diurnal),
- mean diurnal IOP (8-hour diurnal),
- change from Baseline in mean diurnal IOP (8-hour diurnal),
- percentage change from Baseline in mean diurnal IOP (8-hour diurnal).

Where multiple IOP assessments are made on the same day, mean diurnal IOP (12-hour diurnal) is defined as the average of all multiple assessments (Pre T_0 is excluded from the calculation). Mean diurnal IOP (8-hour diurnal) is defined as the average of all assessments up to 04:00pm (Pre T_0 is excluded from the calculation). The visit at which a subject is missing more than (>) 2 assessments for the calculation of mean diurnal IOP will be excluded from the analysis in the PP population.

The number and percentage of subjects with IOP ≤18 mmHg will be summarized by visit, timepoint and treatment group. The 2-sided 95% CI will be calculated using the Clopper-Pearson method. In addition, the difference in proportions between treatments (H-1337 vs Timolol) will be calculated and summarised by visit, timepoint and treatment group (for each of the H-1337 groups). The 2-sided 95% CI for the difference in proportions will be computed using the Wald method.

A similar analysis will be performed for the following 2 endpoints:

- number and percentage of subjects with mean diurnal IOP (12-hour diurnal) ≤18 mmHg, and
- number and percentage of subjects with mean diurnal IOP (8-hour diurnal) ≤18 mmHg.

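### The SAP does not list the visits in the primary IOP model; adding the Day 7 and Day 14 readings is a cheap, low-priority safeguard against a small shift at Day 28

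*SAP*

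**What the plan says.** - **Endpoint (SAP 4.11.1).** "Change from Baseline in IOP (mmHg) at Day 28 and Day 1 (on-treatment time points) in the study eye is the primary efficacy endpoint".
- **Model (SAP 4.11.1).** For the between-arm differences, "A time-matched longitudinal model adjusting for baseline and including a random effect for subject will be used". No visits are listed. The text goes on: "The model will also be tested for treatment by visit and treatment by time points interactions", and "If no interactions are detected, the main effect model will be used". The covariance is unstructured, with a fallback: "If convergence is not achieved, a compound-symmetry structure will be used (TYPE=CS".
- **Tested cells.** SAP 4.3 tests nine cells (five at Day 28, four at Day 1). Protocol 8.4 tests seven (four and three, without +12 h). Neither tests Day 7 or Day 14. All cells must meet the 1.5 mmHg margin, and the arms are tested in the order 1.0% b.i.d., 0.6% b.i.d., 1.0% q.a.m.
- **Day 7 and Day 14 (SAP 4.11.2).** "Change from Baseline in IOP at Day 7 and Day 14 in the study eye will be summarised by visit, timepoint and treatment group", by ANCOVA, as a secondary analysis. Protocol Table 1 schedules Pre-T0 IOP at both visits for every subject.
- **Missing data (SAP 4.2).** "Missing data will not be imputed".
- **Withdrawal (Protocol 4.3).** One ground for withdrawal from study drug is: "Experiences glaucomatous progression and/or unacceptable IOP elevation, per the discretion of the investigator". The protocol asks that withdrawn subjects attend the remaining visits. It also calls them to an Early Termination visit within 14 days of the last dose. The SAP gives that visit no role.

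**The concern.** A likelihood-based repeated-measures model allows for dropout only through the outcomes it contains. If Day 7 and Day 14 are left out, a missing Day 28 value is informed by baseline and by the readings taken within hours of the first dose. A high Day 7 or Day 14 IOP that led to the withdrawal has no influence.

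Suppose the H-1337 arm has more subjects with high IOP, through a worse mean or a heavier upper tail, and more of them leave and miss Day 28. The H-1337 mean at Day 28 then looks better than it is. In a non-inferiority trial that is the unfavourable direction.

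There is also a plain question of specification. Two programmers could fit different primary models from this text, one with Day 7 and Day 14 and one without.

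**Working it through.** **1. The plan's own figure.** The documents give no figure for this shift. The nearest is the sample size (SAP 3.3: limit 2 mmHg, SD 3.0, one-sided alpha 0.05, power 90%): n = 2 x 3.0^2 x (1.645 + 1.282)^2 / 2^2 = 38.6, so 39 per arm. With the noncentral t, 40 per arm gives 90.5% and 45 gives 93.2%; 45 / 0.9 = 50. The figure reproduces. SD 3.0 and 45 per arm are carried forward.

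**2. Does the text settle the visits?** The treatment-by-visit test does not, because Day 1 and Day 28 are already two visits. The mention of each post-randomization visit belongs to the ANCOVA sentence. SAP 4.11.2 gives Day 7 and Day 14 their own ANCOVA. Exclusion is therefore the natural reading, but it is not stated.

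**3. Assumed inputs (not in the documents).**
- SD 3.0 is taken as the residual SD.
- IOP-driven withdrawal is 3-10% on H-1337 and 0.8-4.4% on timolol by the same cutoff.
- Correlation of Day 1 with later visits is 0.3-0.5 (mid 0.4), among later visits 0.6-0.8 (mid 0.7), and within a day 0.8.
- Withdrawal follows a Day 14 cutoff, a Day 7-or-14 cutoff, a noisy mean of the two, or an IOP not in the data.

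**4. Shift at Day 28 Pre-T0.** Large-sample simulation, unstructured covariance, negative values favour non-inferiority:

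| Situation | Shift, mmHg |
|---|---|
| True difference 1.5, all withdrawn miss Day 28, mid correlations | -0.06 to -0.19 |
| Same, full correlation range | -0.04 to -0.25 |
| Same, half of the withdrawn have Day 28, mid correlations | -0.03 to -0.09 |
| True difference 0.75, mid correlations | -0.04 to -0.11 |
| True difference 0, equal SD | none (within 0.01) |
| True difference 1.5, Day 7/14 included, withdrawal follows them | about 0 |
| True difference 1.5, Day 7/14 included, withdrawal follows an unrecorded IOP | -0.01 to -0.05 |

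The zero in the sixth row holds by construction. A separate simulation with logistic withdrawal gave -0.05 to -0.10 (3% timolol vs 7% H-1337) and -0.09 to -0.17 (7% vs 14%), and 0.00 with Day 7/14 included. It also showed:
- Equal means but H-1337 SD 3.5: -0.077 - 0.009 = -0.086.
- Equal means but H-1337 SD 4.0: -0.197 - (-0.004) = -0.193.
- H-1337 better by 1.0: -0.946 - (-0.998) = +0.052, against H-1337.

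**5. One cell.** SE = 3 x sqrt(2/45) = 0.632. Error = Phi(-1.96 - shift/SE). For -0.06: Phi(-1.96 + 0.095) = 0.031. For -0.19: Phi(-1.96 + 0.301) = 0.049. Nominal is 0.025. This is approximate, because the SE is fixed and ignores the missing values. Simulated trials of 50 per arm at 7% vs 14% withdrawal gave 2.9-4.0% without Day 7/14 and 2.0-2.2% with them.

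**6. All cells of one arm.** Multivariate normal draws, shift added at the Day 28 cells:
- All Day 28 cells at 1.5: 0.006-0.011 instead of 0.005 (seven cells); 0.005-0.009 instead of 0.004 (nine).
- Only Pre-T0 at 1.5, the rest equal: 0.026-0.041 instead of 0.022 (seven); 0.026-0.040 instead of 0.021 (nine).

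**7. The fixed sequence.** A Pre-T0-only deficit is most plausible for the q.a.m. arm. Its evening drop is placebo (Protocol 3.1), the morning drop follows the Pre-T0 reading (Protocol 5), and the animal effect is put at upwards of 8-12 hours (Protocol 1.4). That arm is row 3, reached only after both b.i.d. arms pass every cell. With a shared timolol arm, the chance of reaching and falsely passing row 3 is:

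| b.i.d. arms vs timolol | Seven cells |
|---|---|
| equal | 0.013-0.019 instead of 0.011 |
| 0.5 mmHg better | 0.023-0.034 |
| 1.0 mmHg better | 0.026-0.040 |

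With nine cells and equal b.i.d. arms it is 0.012-0.018 instead of 0.010.

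**8. Side effects of adding the visits.**
- Unstructured parameters are k(k+1)/2: 7 to 9 cells gives 28 to 45, and 9 to 11 gives 45 to 66.
- Under compound symmetry, at 10% withdrawal and a true difference of 1.5, the shift is -0.02 to -0.12 with Day 7/14 and -0.06 to -0.20 without.
- In a pooled main-effect model with an assumed 1.5 deficit at trough only, adding the two trough readings moves the common effect from 0.13-0.18 to 0.36-0.49.

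**The case against.** The strongest case against is that this is an ambiguity in an otherwise valid likelihood analysis, with every driver of the shift assumed. The documents give no IOP-withdrawal rate, no difference between arms and no correlations. Rates may be low: all arms are active, treatment lasts 28 days, and subjects have already been through a washout of up to 6-7 weeks, where needed, to an IOP of 23-32 mmHg. Withdrawn subjects are asked to keep attending, and where Day 28 is obtained this shift does not arise. At 3% withdrawal the shift is only 0.04-0.11 mmHg. The change is also more than one line, since it is safe only if the main-effect fallback is kept away from the tested differences. And the model's current detail was added after regulatory comments (SAP Summary of Changes).

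Most of this stands, and it sets the priority. It does not remove the gap: the visit list is absent, and the omitted readings are already collected.

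Three stronger readings are tempting and not supported:
- **That the trial's false-positive rate rises to 0.03-0.05, or to 0.026-0.041.** The first range is for one cell taken alone. The second treats row 3 as if it were tested alone. The all-cells rule and the fixed sequence (SAP 4.3, Protocol 8.4) keep the figure below 0.025 unless the b.i.d. arms are clearly better than timolol.
- **That the shift needs H-1337 to be worse on average.** A heavier upper tail with equal means is enough, and the shift reverses if H-1337 is better.
- **That the SAP excludes Day 7 and Day 14.** It does not say so; exclusion is inferred from SAP 4.11.2.

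**Conclusion.** The point holds as a cheap improvement with a small effect. The primary model's visits are not listed, and the natural reading leaves out Day 7 and Day 14. A shift toward non-inferiority then needs both more high-IOP withdrawal on H-1337 than on timolol and missing Day 28 values in those subjects.

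Under the assumed 3-10% withdrawal and mid correlations it is about 0.06-0.19 mmHg at a true difference of 1.5. That is 4-13% of the margin (0.06/1.5 and 0.19/1.5) and 0.1-0.3 of the SE (0.06/0.632 and 0.19/0.632). Day 1 cells are unaffected. Including the two visits under unstructured covariance brings the shift to about zero when withdrawal follows those readings, and reduces it otherwise.

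The formal conclusion is well protected. The exception is a Pre-T0-only deficit in the q.a.m. arm combined with b.i.d. arms clearly better than timolol. Confidence is moderate, because the rates and correlations are assumptions. Low priority.

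**What to change.** In SAP 4.11.1:
- List the visits and time points in the longitudinal model.
- Include Day 7 and Day 14 Pre-T0 IOP as additional outcomes, with treatment effects specific to each visit and time point.
- State that the main-effect fallback does not apply to the tested differences, so that the added trough readings are not averaged into them.
- Test only the prespecified Day 1 and Day 28 cells, after reconciling the protocol's seven with the SAP's nine.

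**Cost.** SAP wording and programming; no new data. SAP Section 1 allows amendment before database lock. The larger covariance matrix makes the compound-symmetry fallback somewhat likelier, and the gain there is only partial.

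**Not covered.** How Day 28 IOP is handled after other IOP treatment is started (Protocol 4.4) and how Early Termination readings are used (Protocol 4.3) are separate questions. The SAP should state each in its own place.

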3. STUDY DESIGN

3.1 Study Design

The trial will evaluate the safety and efficacy of 3 dose regimens of H-1337 (0.6% b.i.d., 1.0% b.i.d. and 1.0% q.a.m., and timolol maleate (0.5%, b.i.d.) OU for 28 days (\pm 2-day allowable window for Day 28).

Approximately 200 subjects will be randomized and dosed for 28 days. The parallel group, double-masked, active-controlled study will include the following dosing cohorts:

- H-1337 0.6% Ophthalmic Solution b.i.d. (n=50)
- H-1337 1.0% Ophthalmic Solution b.i.d. (n=50)
- H-1337 1.0% Ophthalmic Solution q.a.m. and H-1337 placebo q.p.m. (n=50)
- Timolol 0.5% Ophthalmic Solution b.i.d (n=50)

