3.4 Trial Treatment

Subjects will receive one of four dosing arms: H-1337 (0.6% b.i.d., 1.0% b.i.d. and 1.0% q.a.m. with H-1337 placebo q.p.m.), and timolol maleate (0.5%, b.i.d.) OU for 28 days . IP will be administered bilaterally throughout the trial.

The IWRS will assign a kit number to subjects who qualify for randomization. Each IP kit will contain 3 inner cartons. The first carton containing 2 pouches (each pouch containing 1 a.m. and 1 p.m. bottle) will be dispensed on Day 1 (Baseline). The second carton will be dispensed to the subject on Day 14. The third carton will serve as a back-up should the subject require a replacement carton.

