IP Administration and Compliance: The first dose of study IP will be administered by study staff after the IOP measurement at T₀ on Day 1. Subjects will self-dose for the remainder of the trial except on study visit days when subjects will be instructed to refrain from self-dosing prior to the visit and the study morning IP will be administered by the unmasked dosing coordinator after the related IOP measurements; evening IP will be self-dosed (out of view of study staff) after the related IOP measurements. Compliance will be assessed at applicable visits by asking the subject their recollection of any missed doses. Confirmation of compliant IP dosing the evening prior to a study visit must be confirmed or the visit should be rescheduled. If the subject reports missing more than 4 doses since the prior visit, a Protocol Deviation will be documented and the subject will be counseled on IP compliance.

Heart Rate and Blood Pressure (BP) Measurements: Both systolic and diastolic blood pressure should be recorded. The same type of device and cuff must be used throughout the study on the same subject. An appropriate cuff size with a bladder encircling at least 80% of the upper arm should be used to ensure accurate measurements.

Blood pressure will be measured using the most ideal conditions possible given the subject's medical condition and age. If possible, the same arm should be used throughout the study. Blood pressure should be measured after sitting in a seated position for 5 minutes. Heart rate measurements will be measured by radial pulse for at least 30 seconds. The subject should be in a seated and relaxed state. An automated blood pressure unit may be used to measure the heart rate.

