3.3 Sample Size Justification

The sample size is driven by interest in the IOP lowering effect of H-1337. The study is designed to test whether one or more concentrations of H-1337 are non-inferior to the timolol control in the reduction of IOP. As benefit is represented by a negative number, non-inferiority is achieved when the upper limit of the confidence interval of the difference in treatment (H-1337 minus Timolol) is strictly lower than the non-inferiority margin.

A sample size of 45 subjects per group will allow for at least 90% power to establish non-inferiority of H-1337 over Timolol based on a non-inferiority limit of 2 mmHg, a standard deviation of 3.0 mmHg and a 1-sided t-test (alpha=0.05).

Assuming that 10% of the subjects will not be eligible in the Intent-to-Treat (ITT) population, a total of 50 subjects per group is required.

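### Day 1 contrasts with timolol are estimated separately for two 1.0% arms that have had identical treatment at those readings, which costs avoidable precision in the gatekeeping test

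*SAP*

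**What the plan says.** Protocol 3.4 lists the two high-concentration regimens as "1.0% b.i.d. and 1.0% q.a.m. with H-1337 placebo q.p.m". The morning drop is the same in both arms; the evening drop is active in one and placebo in the other. Protocol 5 (IP Administration and Compliance) has staff give the first dose on Day 1 after the 8 am pressure reading, and on visit days "evening IP will be self-dosed (out of view of study staff) after the related IOP measurements".

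SAP 4.11.1 takes Day 1 and Day 28 change from baseline as primary. From a longitudinal model with a random subject effect, "the differences between treatments (H-1337 vs Timolol) will be calculated for each H-1337 treatment group". SAP 4.3 requires the upper 95% limit to be below 1.5 mmHg at "all 5 time points at Day 28 and all 4 ontreatment time points at Day 1" for Rows 1 to 3 of Table 1. Protocol 8.4 has the same structure without the 12-hour readings: four at Day 28 and three at Day 1. Row 1 is 1.0% b.i.d., Row 2 is 0.6% b.i.d. and Row 3 is 1.0% q.a.m.; a failed row stops formal testing.

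Neither document pools or constrains the two 1.0% arms on Day 1, or says how to read them if their Day 1 results disagree.

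**The concern.** The +2, +4, +8 and (where taken) +12 hour readings on Day 1 all precede the first evening dose. They therefore come from one treatment given to about 100 randomized subjects, but each 1.0% contrast with timolol uses only the 50 in its own arm. The model is not told that the two arms share an expected value at these readings.

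Three of the seven readings that must all pass in Protocol 8.4 (four of nine in SAP 4.3) thus carry noise that could be removed without another subject. This falls on Row 1, which gates every later test. The tables may also show two different Day 1 answers for the same first dose, with no rule for interpreting them.

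**Working it through.** **Inputs.** SAP 3.3 gives SD 3.0 mmHg and 45 evaluable per group; Protocol 3.1 gives 50 per arm; SAP 4.3 gives the 1.5 mmHg threshold and the 2-sided 95% interval. Assumptions not in the documents: a true difference of 0 (0.5 mmHg as an alternative), and equal correlation ρ between readings, varied from 0.3 to 0.7.

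**The plan's own figure.** SAP 3.3 states: "A sample size of 45 subjects per group will allow for at least 90% power", with a "non-inferiority limit of 2 mmHg, a standard deviation of 3.0 mmHg and a 1-sided t-test (alpha=0.05". The SE is 3√(2/45) = 0.632, 2/0.632 = 3.162, and Φ(3.162 − 1.645) = 93.5% (93.2% with the t distribution). The claim is reproduced, and 45/0.9 = 50. With the threshold and interval actually used, one reading with 45 per arm has power Φ(1.5/0.632 − 1.96) = 66% (65% with t).

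**Precision on Day 1.**

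| | Separate arms | Shared 1.0% mean |
|---|---|---|
| SE, 50 per arm | 3√(1/50 + 1/50) = 0.600 | 3√(1/100 + 1/50) = 0.520 |
| SE, 45 per arm | 3√(1/45 + 1/45) = 0.632 | 3√(1/90 + 1/45) = 0.548 |
| 95% half-width (1.96 × SE), 50 per arm | 1.18 | 1.02 |
| Pass chance per reading, 50 per arm | 70% | 82% |
| Pass chance per reading, 45 per arm | 65% | 78% |

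The variance ratio is 0.600²/0.520² = 0.36/0.27 = 1.33, and the interval-width ratio is 0.600/0.520 = 1.15. Pass chances use the noncentral t.

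**Effect on Day 28.** In a joint model the shared Day 1 mean marks the Day 1 gap between the two arms as chance and corrects Day 28 for it. With k Day 1 readings and equal correlation, the Day 1 readings explain R² = kρ²/(1 + (k − 1)ρ) of the variance of a Day 28 reading. The variance of a 1.0% arm's Day 28 mean then falls by the factor 1 − R²/2. With k = 3 and ρ = 0.5, R² = 0.75/2 = 0.375 and the contrast SE is 3√((1 + 0.8125)/50) = 0.571 instead of 0.600. It is 0.587 at ρ = 0.3 and 0.552 at ρ = 0.7.

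**Chance that 1.0% b.i.d. passes all of Row 1** (simulation, true difference 0, separate → shared):

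| | ρ = 0.5 | ρ = 0.6 | ρ = 0.7 |
|---|---|---|---|
| 7 readings, 50 per arm | 31% → 38% | 36% → 45% | 41% → 51% |
| 7 readings, 45 per arm | 25% → 32% | 30% → 38% | 35% → 45% |
| 9 readings, 50 per arm | 27% → 34% | 32% → 41% | 38% → 48% |

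The choice between normal and t critical values moves these by about one point. At ρ = 0.3 with 7 readings the gain is about 5 to 6 points. With within-day correlation 0.6 and between-day correlation 0.3 it is 28% → 35% (50 per arm). If only the Day 1 contrasts were pooled and Day 28 were left as it is, it would be 31% → 35% (ρ = 0.5, 50 per arm). With a true difference of 0.5 mmHg and ρ = 0.5 it is 6% → 8% (50 per arm) or 5% → 6% (45 per arm).

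**Disagreement between the two arms as reported.** Suppose each arm is classified by whether all three Day 1 readings meet the 1.5 criterion. At a true difference of 0, the arms then disagree in about 32 to 35% of trials across the correlations examined. At a single reading it is 28% (50 per arm) or 30% (45 per arm).

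**The case against.** Comparing each randomized arm with control is unbiased, follows the assigned treatment as SAP 3.4.2 requires, and is protected by the fixed sequence. Nothing in the documents is contradictory here, and the model was revised after regulatory comment. This stands: the point concerns efficiency and coherence, not error.

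A reader might infer that half of the 1.0% data are discarded. They are not. Each arm's data serve its own contrast, and because the timolol arm is unchanged the avoidable part is a quarter of the present contrast variance (0.36 to 0.27).

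A reader might also infer that the trial can formally return opposite verdicts on one dose. The documents do not support that, because a formal verdict is for a regimen over Day 1 and Day 28 together. Row 3 is tested only if Rows 1 and 2 pass, which happens in about 9 to 30% of simulated trials (ρ 0.5 to 0.8, 45 or 50 per arm, 7 or 9 readings, true difference 0). Row 3 is then reached and q.a.m. fails a Day 1 reading in about 3 to 6% of trials; Day 1 is the sole reason for its failure in about 1 to 2%. The reverse cannot arise formally. The disagreement in about a third of trials describes reported results only.

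Two further limits stand. SAP 4.11.1 reverts to a main-effect model if no interaction is detected, and then there may be no separate Day 1 estimate to improve. A shared Day 1 mean also lets the other arm's Day 1 data influence each Day 28 estimate through the fitted covariance.

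A mix-up of morning and evening bottles could in principle break the Day 1 equality, because only the q.a.m. kit contains placebo. That is remote for a first dose given in the office by staff.

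**Conclusion.** The point holds as a specific, modest loss of efficiency. The two 1.0% arms are identically treated at every Day 1 post-dose reading, and estimating them apart makes the Day 1 contrast variance a third larger than it need be. The equality rests on randomization and identical in-office dosing. The SE ratio depends only on the allocation and a common SD.

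The gain in passing Row 1 depends on more: about 5 to 10 points for ρ between 0.3 and 0.7 at a true difference of 0, and about 1 to 3 points at 0.5 mmHg. Row 1 remains more likely to fail than to pass in nearly all of these scenarios, so this change does not repair the trial's power. The conclusion is the same for seven or nine readings; that difference between protocol and SAP is a separate matter.

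**What to change.** Amend SAP 4.11.1 and 4.3 before unmasking:

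- Fit the longitudinal model with a mean for each treatment, visit and time point. Constrain the two 1.0% arms to one mean at each Day 1 post-dose time point, and keep their Day 28 means separate.
- Use that shared Day 1 difference from timolol in Rows 1, 3, 4 and 6 of Table 1.
- State that the interaction tests and the main-effect fallback do not replace these time-point estimates.
- Keep the as-randomized Day 1 summaries as descriptive, and report the unconstrained model as a sensitivity analysis.

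The cost is somewhat more model specification and some reliance of the Day 28 estimates on the fitted covariance. No dose, visit, margin or sample size changes. Because Rows 1 and 3 would share Day 1 data their results become more correlated, which a fixed sequence permits. Pooling chosen after unmasking would look selective, so if the sponsor wants this gain it must be specified while the study is still masked.
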